1. INTRODUCTION

1.1. Background

Kidney cancers account for about 86% of cancers of the kidney/renal pelvis [Chow, 1999], the incidence of renal cell carcinoma (RCC) has been increasing steadily in nearly all regions of the world [Murai, 2004]. Advanced RCC (Stage IV) is generally resistant to chemotherapy and hormonal therapy, with responses usually not exceeding 10% for any cytotoxic regimen that has been studied in adequate numbers of subjects [Motzer, 2000]. RCC has been considered an immunosensitive tumor and over the past several decades immune-based therapies with interleukin-2 (IL-2) and interferon α (IFN α), have been extensively investigated in subjects with advanced RCC. Collectively, the objective response rate seen with IFN α treatment is approximately 10-15%; and the responses are rarely complete or durable [McDermott, 2004]. The overall survival seen with high-dose IL-2 is similar to that of IFN α [McDermott, 2005].

Clear cell RCC, which constitutes approximately 75 - 80% of RCC, has been found to be associated with a high incidence of biallelic inactivation of the von Hippel-Lindau (VHL) tumor suppressor gene [Kim, 2004]. VHL plays a key role in regulating the angiogenic pathways that are mediated by the hypoxia-inducible factor-1 α (HIF-1 α). HIF-1 α is usually activated under hypoxic conditions within a tumor which leads to transcription of various down-stream angiogenic growth factors and cytokines, most notably, vascular endothelial growth factor (VEGF), platelet-derived growth factor (PDGF), transforming growth factor- α (TGF α) and erythropoietin. These trigger various signal transduction pathways resulting in initiation and augmentation of tumor angiogenesis. [Geoarge, 2003]

Angiogenesis is critical for the growth and survival of human tumours. [Karamysheva, 2008] The process is controlled by a balance between pro-angiogenic factors (e.g. VEGF, PDGF and FGF) and anti-angiogenic factors (e.g. angiostatin, endostatin and thrombospondin) [Distler et al, 2003] VEGF is the most potent pro-angiogenic factor, and is overexpressed in virtually all solid tumours. [Ferrara et al, 1997]

Pazopanib (Votrient) is a potent multi-target receptor tyrosine kinase inhibitor of vascular endothelial growth factor receptors (VEGFR) -1, -2 and -3, platelet-derived growth factor receptors (PDGFR) $-\alpha$ and $-\beta$, and stem cell factor receptor (c-kit). [kumar, 2007] VEGFR regulates angiogenesis [Kerbel, 2008] and PDGFR regulates angiogenesis and proliferation of some tumour cells [Yu et al, 2003, Homsy et al, 2007]. And c-Kit regulates cellular proliferation, survival and metastasis. [Demetri, 2001] Pazopanib targets these key molecules involved in tumour angiogenesis. [Sonpavde et al, 2008] Pazopanib is a more selective multikinase inhibitor compared with sunitinib. [Kumar et al, 2009] Besides VEGFR, PDGFR and c-Kit, sunitinib inhibits 49 additional kinases. By contrast, pazopanib inhibit seven additional kinases. And pazopanib has a greater affinity to VEGFR-2 than sunitinib. [Kumar et al, 2009, Karamen et al, 2008]

Clinical efficacy and safety of pazopanib in treating advanced RCC patients have been established in a randomized double-blind placebo-controlled Phase III study that enrolled 435 treatment-naïve or cytokine-pretreated subjects. PFS was significantly prolonged with pazopanib compared with placebo in the overall study population (median, PFS 9.2 v 4.2 months; hazard ratio [HR], 0.46; 95% CI, 0.34 to 0.62; $P < 0.0001$), the treatment-naïve subpopulation (median PFS 11.1 v 2.8 months; HR, 0.40; 95% CI, 0.27 to 0.60; $P < 0.0001$), and the cytokine-pretreated subpopulation (median PFS, 7.4 v 4.2 months; HR, 0.54; 95% CI, 0.35 to 0.84; $P < 0.001$). The objective response rate was 30% with pazopanib. [Sternberg et al, 2010]

Soft Tissue Sarcoma (STS) is a rare group of heterogeneous mesenchymal cancers originating from connective tissue. The annual incidence of STS is around 2-3/100,000. Overall, STS account for approximately 1% of all malignancies, while they give rise to 2% of the total cancer-related mortality. The 5-year survival in Europe for adult STS (excluding visceral STS) averages 60%, with substantial geographic variations. [Storm et al, 1998] The median survival time in patients with metastatic STS is usually < 12 months.

Surgery is usually the first line of management for localized disease. Standard treatment is generally a wide surgical excision or even more radical surgery of the primary tumor combined with adjuvant radiotherapy in selected cases. The addition of post-operative radiotherapy appears to reduce the rate of local recurrence. [Leibel et al, 1982] However, even optimal local treatment does not prevent the occurrence of distant metastases in many patients, especially those with high-grade tumors. Although the effect of adjuvant chemotherapy has been studied by several groups, the results do not allow to draw any final conclusions. An international meta-analysis indicated an effect of adjuvant systemic treatment on progression free survival but did not show a significant effect on overall survival. [Sarcoma Meta-analysis Collaboration, 1997] STS metastasizes primarily to the lungs but also to bone, liver and other organs, depending on the subtype. Chemotherapy is widely used in the treatment of irresectable advanced disease, basically with a palliative intent, as most initially chemotherapy-sensitive patients will ultimately relapse and present at that point with chemotherapy-resistant disease.

Clinical efficacy and safety of pazopanib in soft tissue sarcoma patients have been established in a randomized double-blind placebo-controlled Phase III study that enrolled 369 randomized pts (246 pazopanib, 123 placebo). The progression-free survival (PFS) per independent review is significantly prolonged with pazopanib (median: 20 vs 7 weeks; HR=0.31, 95% CI 0.24-0.40 ; P<0.0001). The interim analysis for overall survival shows a statistically non-significant improvement of pazopanib vs placebo (median: 11.9 vs 10.4 months, HR=0.83, 95% CI 0.62-1.09). Main on-therapy grade 3-4 toxicities in the pazopanib vs placebo arm respectively: fatigue (13%, 6%), hypertension (7%, nil), anorexia (6%, nil), and diarrhea (5%, 1%). Similarly, thromboembolic events (grade 3-5) (3%, 2%), LVEF drop of >15% (8%, 3%). [Van et al, 2011]

Despite the rigorous requirements of the drug approval process, the full range of a drug's risks cannot be evaluated until that drug is marketed and used in the real world of clinical practice. In premarketing studies, only small numbers of carefully screened and otherwise healthy subjects who are treated for only short periods and monitored only for short-term outcomes. These kind of limitations in premarketing studies make it necessary to conduct postmarketing studies to explore both the effectiveness and the risks of medications as they are used in more realistic settings. Korean regulatory authority has requested the marketing authorization holder to conduct regulatory-mandated post-marketing surveillance (PMS) for collecting safety and effectiveness data of product in Korean patients since 1995. Therefore, this Votrient PMS is to meet Korean regulatory requirements.

2. OBJECTIVES

2.1. Primary objective

- The primary objective of this PMS is to monitor the incidence of adverse events administered Votrient in Korean patients.

2.2. Secondary objective

The secondary objectives are to identify as follow in cancer patients administrated Votrient .

- Unexpected adverse drug reaction (ADR) and serious adverse events(SAE)
- Effectiveness

3. PMS DESIGN OVERVIEW

- Non-interventional, open-label, single group, multicenteric post-marketing surveillance in Korea.
- Indication:

Study identifier: 115578
GlaxoSmithKline Korea

Protocol Ver.2

1. Advanced renal cell carcinoma
 2. Advanced soft tissue sarcoma who have received prior chemotherapy : Adipocytic soft tissue sarcoma or gastrointestinal stromal tumors has not been demonstrated.
- Subjects treated and/or will be treated with Votrient according to the prescribing information will be enrolled.
 - Control: None
 - Data collection: Standardized electronic Case Report Form (e-CRF)

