4.2. Eligibility criteria

The investigators enroll advanced renal cell carcinoma or Soft Tissue Sarcoma (STS) patients administered Votrient at the site.

All subjects must satisfy the following criteria at PMS entry according to KFDA PMS regulation:

- Subject who received Votrient as described the prescribing information
- Subject who don't have contraindication according to the prescribing information
- Subject is willing and able to provide written informed consent

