9.4. Recording of AEs and SAEs

When an AE/SAE occurs, it is the responsibility of the investigator to review all documentation (e.g., hospital progress notes, laboratory, and diagnostics reports) relative to the event. The investigator will then record all relevant information regarding an AE/SAE on the CRF.

It is not acceptable for the investigator to send photocopies of the subject's medical records to GSK in lieu of completion of the appropriate AE/SAE CRF pages. However, there may be instances when copies of medical records for certain cases are requested by GSK. In this instance, all subject identifiers will be blinded on the copies of the medical records prior to submission to GSK.

The investigator will attempt to establish a diagnosis of the event based on signs, symptoms, and/or other clinical information. In such cases, the diagnosis should be documented as the AE/SAE and not the individual signs/symptoms.

From the time a subject agree to his or her participating in this PMS until one month after he or she has completed Votrient treatment (including any follow-up period), AE/SAE will be reported promptly to GSK.

Any signs and symptoms present at the time the first dose is administered will be documented as baseline signs and symptoms. Any medical occurrences which present after administration of the medication and on or before the final follow up visit must be reported as Adverse Events. All AEs must be recorded irrespective of whether they are considered drug related. At each visit/assessment in the period defined above, AEs/SAEs will be evaluated by the investigator and recorded. Any AEs/SAEs already documented at a previous assessment and designated as ongoing, should be reviewed at subsequent visits as necessary. If these have resolved, this should be documented. If an AE changes in intensity then the maximum intensity should be captured in the CRF.

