9.9. AE/SAE after end of surveillance

AE/SAE is defined as any event that occurs outside of the AE/SAE detection period as defined in the protocol. (Refer to Section 9.4)

Investigators are not obligated to actively seek AEs or SAEs in former subjects. However, if the investigator learns of any SAE, including a death, at any time after a subject has been discharged from the surveillance, and considers the event reasonably related to the drug, the investigator will promptly notify GSK.

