11.6.3. Analysis of effectiveness

The percentage of subjects after administration of Votrient will be tabulated.

The percentage of subjects after administration of Votrient by age, gender, past medical history, concomitant medication, the elderly, allergy, diagnosis and indication will be calculated.

- These endpoints below by indication will be calculated **Overall Response Rate**

This is defined as the percentage of subjects achieving either a complete (CR) or partial (PR) tumor response. The response rate will be calculated from the evaluation by treating physicians of best response which records of PR and CR only. Subjects with unknown or missing response will be treated as not evaluable; i.e. they will be included in the denominator when calculating the percentage. Response rates will be compared between treatment arms using stratified Fisher's exact tests. Approximate 95% confidence limits for the difference in response rates will be calculated. Exact 95% confidence limits for the tumor response rates in each arm will also be calculated

- **Progression-free survival**

This is defined as the time from initiation of medication until the earliest date of disease progression or death due to any cause, if sooner. Date of disease progression will be based on data that is captured on the case report form. At the time of analysis, for subjects who have not progressed or died, progression-free survival will be censored at the date of discontinuation of medication.

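### Already-treated subjects may enrol, but Section 9.4 gives two conflicting AE start points for them, and PFS runs from first dose with no late entry

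*Protocol*

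**What the plan says.** **Who enters.** Protocol Section 3 states that "Subjects treated and/or will be treated with Votrient according to the prescribing information will be enrolled". Section 4.2 uses the past tense, "Subject who received Votrient as described the prescribing information", and adds the condition "Subject is willing and able to provide written informed consent". No waiver is stated for patients who have died. Nothing requires a subject to be progression-free, or still on drug, at consent.

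**When AE collection starts.** Section 9.4 has prompt reporting run "From the time a subject agree to his or her participating in this PMS until one month after he or she has completed Votrient treatment". Later in the same section it says "Any medical occurrences which present after administration of the medication and on or before the final follow up visit must be reported as Adverse Events", and then "At each visit/assessment in the period defined above, AEs/SAEs will be evaluated by the investigator and recorded". Section 9.9 points back to Section 9.4 for the detection period. Table 1 in Section 5.1 marks AEs during treatment and at the last observation, but not at baseline. The primary endpoint in Section 11.1 is the occurrence of AEs following drug administration, by indication.

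**When PFS starts.** Section 11.6.3 says "This is defined as the time from initiation of medication until the earliest date of disease progression or death due to any cause". Subjects without an event are censored when medication is discontinued. No late-entry rule is given.

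**The concern.** For a subject who consents before or at first dose, these clocks nearly coincide. For one who consents later they separate: the primary endpoint and PFS start at first dose, while one of the two AE rules starts at consent.

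Two things are at stake. First, sites that follow different sentences of Section 9.4 would collect different primary-endpoint data on the same kind of patient, and AEs never collected cannot be restored at analysis. Second, the interval from first dose to consent is free of death by design, and free of progression for those who enter before progressing. Counting that interval as ordinary time at risk pushes PFS upward. This is selection, so enrolling 3000 subjects does not reduce it.

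**Working it through.** The plan has no figure of its own to reproduce: 3000 is a regulatory number (Section 11.4), with no precision or power target behind it.

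**1. AE window for a subject who consents after first dose**

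| | Consent rule (9.4) | Administration rule (9.4) |
|---|---|---|
| AE between first dose and consent | outside the window | reportable retrospectively |
| Patient who died before consent | absent | absent |
| Agrees with Section 11.1 | no | yes |
| Step in Table 1 that collects it | not applicable | none at baseline |

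The share lost under the consent rule depends on onset times, which the documents do not give. If time to first onset is exponential with an assumed median of 8 weeks, the share before consent is 1 − 0.5^(lag/8): 29%, 50% and 65% for lags of 4, 8 and 12 weeks. Under the administration rule these events are reportable.

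**2. PFS if every late entrant is progression-free at consent**

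Inputs from Section 1.1: median PFS m = 9.2 months (RCC) and 20 weeks, i.e. 20/4.345 = 4.6 months (STS). Assumed: exponential PFS; a share f of the source patients already treated (25-100%); consent lag uniform on 0 to M months (M = 3 or 6).

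With λ = ln 2/m, a late entrant is still progression-free at consent with probability K = (1 − e^(−λM))/(λM). The retained share of all source patients is N = (1 − f) + fK. Beyond time M the naive curve is e^(−λt)/N, so when the median falls after M it is m(1 − log2 N).

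| | f | M | K | N | Naive median | Change |
|---|---|---|---|---|---|---|
| RCC, low end | 25% | 3 | 0.895 | 0.974 | 9.55 | +4% |
| RCC, high end | 100% | 6 | 0.805 | 0.805 | 12.1 | +31% |
| STS, low end | 25% | 3 | 0.805 | 0.951 | 4.9 | +7% |
| STS, high end | 100% | 6 | 0.658 | 0.658 | 7.4 | +60% |

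**3. PFS if late entrants need only be alive at consent (STS)**

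This is all that the entry criteria guarantee. Added inputs: median overall survival of 11.9 months (Section 1.1), and an assumption that 10-30% of PFS events are deaths. The rest are progressions, followed by exponential survival scaled to give the 11.9 months. By simulation, over the same f and M, the naive median runs from 4.67 months (10% deaths, f = 25%, M = 3) to 5.58 months (30% deaths, f = 100%, M = 6). Against 4.60 that is 4.67/4.60 = +1.5% to 5.58/4.60 = +21%.

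**4. Does delayed entry remove the bias?**

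Under the model of step 2 with f = 50% and M = 6, 20,000 enrolled subjects were simulated. The naive medians were 10.6 (RCC) and 5.9 months (STS). A Kaplan-Meier estimate that admits each subject to the risk set only from consent gave 9.1 and 4.6, close to the true 9.2 and 4.6.

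**The case against.** The strongest reply has four parts.

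*AE collection does not simply start at consent.* A reader might infer that early AEs are certainly missed and the primary endpoint understated. The documents do not support that. The consent sentence concerns prompt reporting to the sponsor. The next paragraph of Section 9.4 makes any occurrence after administration reportable, Section 11.1 agrees, and the reference to the period above follows both rules. This stands: the finding is a contradiction, with loss under one reading only. Direction is not assured for every AE either, since subjects who stay on drug until a late consent may have longer exposure and more late AEs.

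*The larger PFS figures need an entry rule that the protocol lacks.* A reader might take +60% as the implied bias. That figure requires every late entrant to be progression-free at consent. A progression before consent can be recorded on the case report form and counted as an event. This also stands, which is why step 3 is shown beside step 2.

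*Late entry may be in an analysis plan not shown here.* This is possible for PFS, although the protocol itself fixes the origin and censoring without mentioning it. It cannot help with AEs that sites were never told to collect.

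*This is descriptive, single-group surveillance and PFS is secondary.* That is true and lowers the severity. The AE window, however, belongs to the primary endpoint.

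**Conclusion.** The point holds as a should-fix. Three things follow from the text alone:

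- Section 9.4 contains two AE start points that diverge for already-treated subjects, and only one of them matches the primary endpoint.
- Patients who died before consent cannot appear under either rule.
- PFS from first dose, without late entry, contains time in which death was impossible by design, so a naive estimate is biased upward.

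The size does not follow from the text. The already-treated share, the consent lag, the AE onset times and the proportion progression-free at consent are all unstated. Under the assumptions above, the STS median of 4.6 months moves to about 4.7-5.6 months when only survival to consent is required, and to 4.9-7.4 months when all late entrants are progression-free. The RCC median of 9.2 months moves to about 9.55-12.1 months in the second case. Established loss of early AEs, or a PFS inflation of any one stated size, would go beyond the documents.

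**What to change.** 1. **AE window.** Reconcile Section 9.4 with Table 1 and Section 11.1 so that the window opens at first dose for every subject. Record the first-dose and consent dates. For subjects who consent later, take AEs in between from the chart and flag them as retrospective.
2. **PFS.** For subjects progression-free at consent, estimate PFS with delayed entry at the consent date. Report separately those who had already progressed, since a delayed-entry analysis cannot use them. Add a sensitivity analysis in subjects who consented at or before first dose.
3. **AE incidence.** Tabulate by consent at or before versus after first dose as a supporting analysis. Keep the full safety population as the main estimate: the early-consent subgroup could be small, and the required sample is the whole 3000.

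The cost is protocol wording, two dates on the case report form, limited chart abstraction and additional supporting analyses. Delayed-entry curves are less stable at early times when few subjects are yet at risk, and they assume that the consent lag is unrelated to later prognosis. None of these changes brings back patients who died before consent, so the report should state that limit.

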4. POPULATION

4.1. Number of subjects

3000 subjects will be enrolled according to the Korean PMS regulation.

4.2. Eligibility criteria

The investigators enroll advanced renal cell carcinoma or Soft Tissue Sarcoma (STS) patients administered Votrient at the site.

All subjects must satisfy the following criteria at PMS entry according to KFDA PMS regulation:

- Subject who received Votrient as described the prescribing information
- Subject who don't have contraindication according to the prescribing information
- Subject is willing and able to provide written informed consent

5. ASSESSMENT OF PMS

5.1. Outline of PMS procedures

Table 1 Overview of PMS procedures

Visit	BASELINE	DURING TREATMENT ¹	LAST OBSERVATION ²
Check eligibility criteria	X		
Cancer information	X		
Demography	X		
Medical history	X		
Concomitant medication	X	X	X
Prescription	X	X	
Adverse events occurrence		X	X
Laboratory Test Results(optional)	X	X	X
Tumor assessments(optional)	X	X	X
Survival			X

1. The every-4week assessment of AE and tumor will be recommended. Disease assessment will be done by the study site's institutional standard.

2. Last observation is recommended to be conducted at 12 months after baseline excluding progression, death, drop-out (e.g. due to unacceptable AE/SAEs) or follow-up loss.

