5.2.3. Last observation

- Safety Assessment
- Concomitant medication
- Laboratory test result
- Tumor evaluation
- Disease progression
- Survival

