8. SUBJECT COMPLETION AND WITHDRAWAL

8.1. Subject completion

All subjects who receive at least one dose of the drug and at least once safety assessment will be safety population. Last observation is recommended to be conducted at 12 months after baseline in order to evaluate safety and effectiveness. If the subject do not return to follow-up visit, all data collected until the date of last contact of the subject will be used for the analysis.

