8.2. Subject withdrawal

Subjects who are withdrawn because of SAEs/AEs must be clearly distinguished from subjects who are withdrawn for other reasons. Investigators will follow subjects who are withdrawn as result of a SAE/AE until resolution of the event. Withdrawals will not be replaced.

A subject is considered a 'withdrawal' from the PMS when no PMS procedure has occurred, no follow-up has been performed and no further information has been collected for this subject from the date of withdrawal/last contact.

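### Progression and death after stopping Votrient without progression are not scheduled for collection, although PFS counts them; Table 1 note 2, 5.2.3, 8.1 and the censoring rule in 11.6.3 should be changed together

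*Protocol*

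**What the plan says.** Four places in the protocol bear on this.

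- **5.1, Table 1 and note 2.** The Survival row has one mark, at last observation. Note 2 recommends that observation at 12 months, "excluding progression, death, drop-out (e.g. due to unacceptable AE/SAEs) or follow-up loss". It does not say whether the observation is then made earlier or not made at all.
- **5.2.3.** The items for the last observation include "Disease progression - Survival". Neither is listed as an item under 5.2.1 or 5.2.2. Tumour evaluation is listed during treatment, and Table 1 marks it optional.
- **8.1.** "Last observation is recommended to be conducted at 12 months after baseline in order to evaluate safety and effectiveness". No exceptions follow, but for a subject who does not return, "all data collected until the date of last contact of the subject will be used for the analysis".
- **11.6.3.** PFS is the "time from initiation of medication until the earliest date of disease progression or death due to any cause, if sooner". Progression dates come from the case report form. Subjects without progression or death are censored at the date they discontinue medication.

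On withdrawals for adverse events, 8.2 adds: "Investigators will follow subjects who are withdrawn as result of a SAE/AE until resolution of the event".

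**The concern.** The PFS definition does not stop at the end of treatment, but scheduled collection can. A subject who stops Votrient at month 2 for toxicity, progresses at month 4 and dies at month 6 has a PFS event under 11.6.3. Note 2 releases that subject from the 12-month observation, and no other scheduled contact would supply the progression date.

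This differs from an ordinary censoring question. Section 11.6.3 censors only subjects who have not progressed or died, so a later progression would count if it were on the form. Whether it counts depends on collection, and an analysis plan cannot restore events that were never recorded. At stake is a named secondary endpoint: if subjects who cannot tolerate the drug do worse afterwards, they leave the data while still event-free and PFS looks better than it is.

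**Working it through.** **1. Can another route supply the missing events?**

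| Route | What it covers | Later progression? | Later death? |
|---|---|---|---|
| 9.4 | AEs/SAEs until one month after treatment | No | Fatal SAEs in that month |
| 8.2 and 9.6 | Follow-up of AEs already recorded | No | As the outcome of such an event |
| 9.9 | SAEs, including deaths, learned of after discharge and considered drug-related | No | Drug-related only |
| 9.1 | Expected progression is excluded from the AE definition | No | – |

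Two kinds of event are left without scheduled capture: progression after stopping, and deaths beyond these windows that are not judged drug-related.

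**2. How large could the effect on PFS be?** The protocol has no figure to reproduce: the 3000 subjects are a regulatory number, and no PFS target or drop-out rate is given. I used a simple model.

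Inputs from section 1.1: median PFS of 9.2 months in RCC and 20 weeks in STS (20/4.345 = 4.60 months).

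Assumptions: constant hazards; toxicity drop-out precedes a PFS event with overall probability p = 0.15 or 0.25; after drop-out the hazard is k times the on-treatment hazard, k = 1 to 3.

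Formulas: L = ln 2 / median; g = L·p/(1−p); a = L + g; b = kL.

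- Reported 12-month PFS, censored at drop-out: exp(−12L)
- True 12-month PFS: exp(−12a) + g·exp(−12b)·[1 − exp(−12(a−b))]/(a−b)

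RCC: L = 0.0753, so the reported value is 40.5%. STS: L = 0.1506, reported 16.4%.

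| | p | k | True 12-month PFS (two terms) | Reported minus true |
|---|---|---|---|---|
| RCC | 0.15 | 2 | 0.345 + 0.039 = 38.4% | 2.1 points |
| RCC | 0.25 | 3 | 0.300 + 0.047 = 34.6% | 5.9 points |
| STS | 0.15 | 2 | 0.119 + 0.020 = 13.9% | 2.5 points |
| STS | 0.25 | 3 | 0.090 + 0.017 = 10.7% | 5.7 points |
| Either | any | 1 | same as reported | 0 |

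A second set of assumptions gives a similar picture. Take 10% to 30% drop-out by month 12 in the absence of progression, and k from 1 up to the inverse of the hazard ratios in section 1.1 (1/0.46 = 2.17 and 1/0.31 = 3.23). The uncollected PFS events then amount to 2.6% to 13.0% of RCC subjects and 3.1% to 13.5% of STS subjects. The true median would be 8.3 to 9.2 months against 9.2 reported (RCC), and 4.2 to 4.6 against 4.6 (STS).

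**3. Does collecting the events suffice?** No. Suppose later events to month 12 are counted while subjects still event-free are censored back at discontinuation, as 11.6.3 says. Drop-outs who do badly then contribute their events, and drop-outs who do well are removed early. Simulating the step 2 model with 2 million subjects at equal hazard, where the present rule is unbiased, 12-month PFS falls:

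- RCC: from 40.5% to 38.3% (p = 0.15) and about 36% (p = 0.25)
- STS: from 16.4% to 13.7% and about 11%

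At k = 2 to 3 the result is still too low, by about 0.4 to 2.5 points.

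**The case against.** The strongest reply is that this is a single-arm, non-interventional safety surveillance in which tumour assessment is optional and PFS is secondary, so follow-up off drug is a design preference. The size also rests wholly on assumed inputs, and at equal hazard there is no bias. In addition, 11.5 limits the effectiveness population to subjects who complete every protocol procedure, which may exclude early drop-outs altogether. All of this stands as a limit on how much weight to give the point. It does not reconcile an any-cause, no-on-drug-limit PFS definition with a schedule that need not record its events.

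Four stronger readings are tempting and are not supported:

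- *Later deaths never reach the case report form.* Too strong: the routes in 9.4, 9.6 and 9.9 capture some of them.
- *Section 8.1 sets a firm 12-month observation that Table 1 breaks.* Both passages only recommend 12 months, and 8.1 itself provides for an earlier last contact. The discrepancy is that 8.1 omits the exceptions in note 2.
- *Note 2 moves the visit forward.* That is the natural reading, but the text does not say so. Moved or omitted, status at 12 months is missing.
- *Closing at progression damages the endpoints.* Progression is itself the PFS event, so nothing is lost there. Later deaths would matter for overall survival, which is not an endpoint in 11.1 or 11.2 and is not analysed in 11.6.

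Nor does 8.2 mean that the data are already at hand: it keeps contact only until the adverse event resolves, and not for tumour status.

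**Conclusion.** The point holds for subjects who stop Votrient without progression. Their later progression, and later deaths not judged drug-related, have no scheduled collection, while the PFS definition counts both. The consequence is PFS reported too high if these subjects fare worse after stopping: by about 2 to 6 points at 12 months under the assumed 15% to 25% drop-out and a 2- to 3-fold hazard, and by nothing at equal hazard. The direction is plausible; the size is illustrative, because the protocol gives neither a drop-out rate nor a hazard after drop-out. The change is worth making, since an analysis plan cannot recover events that were not recorded.

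**What to change.** Make these changes together:

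1. In Table 1 note 2, state what is collected from subjects who stop Votrient without progression. Until month 12, abstract from the chart routine tumour evaluations, date of progression, start of any other anticancer therapy, and vital status. Add no tests or visits.
2. Align 8.1 and 5.2.3 with note 2, so that all three give the same timing, exceptions and items.
3. In 11.6.3, replace censoring at discontinuation of medication with censoring at the last tumour evaluation or last contact without an event. Items 1 and 2 without this would replace a possible upward bias with a downward one.

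No month-12 contact is needed for subjects who have already progressed, since overall survival is not an endpoint. The cost is protocol wording and modest extra data entry at sites for subjects who stop early.
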